8.8. Columbia Suicide Severity Rating Scale (C-SSRS)

The Columbia Suicide Severity Rating Scale (C-SSRS) is a rating-based interview assessment tool that evaluates suicidal ideation and behavior.

The C-SSRS questionnaire includes five subtypes of suicidal ideation, five subtypes of suicidal behavior, and self-injurious behavior without suicidal intent as a standard. Additionally, it includes a suicidal behavior lethality rating and a suicidal ideation intensity rating. It is a safety questionnaire that addresses concerns for various regulatory bodies.

Since this is a small study, with no control arm, C-SSRS data will just be displayed in a listing.

8.9. Other Safety Assessments

Pregnancy Test

Pregnancy test results will be listed by subject.

Neurological Examination

Neurological examination results will be listed by subject.

Viral Safety Test

Viral safety test results for Human immunodeficiency virus (HIV) 1 and 2, Hepatitis B virus (HBV) and Hepatitis C virus (HCV) will be listed by subject.

9. EFFICACY

9.1. General Considerations

Descriptive statistics for continuous and categorical variables will be presented as described in [Section 6.4](#).

Inferential statistical tests will be performed at Type I error $\alpha = 0.05$ (Two-sided). Since this is a single arm, open label study, hypothesis testing will be performed against a historical database by selection of subjects matched on key screening or baseline characteristics.

9.2. Analysis of Primary Efficacy Endpoint

The primary objective and endpoints in the study are assessments of safety. The secondary objective and endpoints are assessments of efficacy.

The first secondary endpoint is considered the primary efficacy endpoint for this study.

Efficacy analyses will be performed using the modified mITT and EE populations. If mITT and EE populations are the same then, all efficacy analysis will be performed using mITT population only.

The primary efficacy endpoint will be a responder analysis to see if subjects improve in walking speed as measured by time to complete T25FW (ft/sec.) or improve in finger (fine manual) dexterity as measured by time to complete the 9-HPT (sec.)

A subject will be defined as a responder to study drug if their T25FW walking speed or 9-HPT improves by 25% or more between baseline and Week 28. An improvement of 25% is considered clinically meaningful for MS patients^{4,6}.

All deaths related to disease progression or treatment will be defined as non-responders.

The T25FW, 9-HPT, LCLA and SDMT are part of the current Multiple Sclerosis Functional Composite (MSFC) and described in Additional detail in [the BCT-101-US Protocol, Sections 15.2.1, 15.2.2, 15.2.3, 15.2.6, and 15.2.7](#) in Appendix 1.

The T25FW is a quantitative mobility and leg function performance test based on a timed 25 foot-walk. It is the first component of the MSFC to be administered at each visit. The subject is directed to one end of a clearly marked 25-foot course and is instructed to walk 25 feet as quickly as possible, but safely. The time is calculated from the initiation of the instruction to start and ends when the subject has reached the 25-foot mark. The task is immediately administered again by having the subject walk back the same distance. T25FW score is the average in seconds of the two successive trials. Subjects may use assistive devices when doing this task. An increase in speed for T25FW is considered an improvement.

The MSFC uses a z-score transformation which will be used in assessing the changes in the MSFC.

The 9-HPT is a brief, standardized, quantitative test of upper extremity function. It is the second component of the MSFC to be administered at each visit. Both the dominant and non-dominant hands are tested twice. The participant is seated at a table with a small, shallow container holding nine pegs and a wood or plastic block containing nine empty holes. On a start command when a stopwatch is started, the participant picks up the nine pegs one at a time as quickly as possible,

puts them in the nine holes, and, once they are in the holes, removes them again as quickly as possible one at a time, replacing them into the shallow container. The total time to complete the task is recorded. Two consecutive trials with the dominant hand are immediately followed by two consecutive trials with the non-dominant hand. A decrease in time to complete the 9-HPT is considered an improvement.

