3.1. INCLUSION CRITERIA

Study participants meeting all of the following criteria will be allowed to enroll in the study:

1. Males and females ages 18 to 65 years old, inclusive, at the Screening Visit
2. Clinical diagnosis of primary or secondary progressive MS (PPMS or SPMS) based on the 2017 revised MacDonald Criteria and have confirmation by the Investigator that the disease has entered the progressive stage at least 6 months prior to enrollment.
3. No evidence of clinical MS relapse or high dose pulse corticosteroid treatment within 6 months prior to screening.
4. Disability status at screening with an Expanded Disability Status Scale (EDSS) 3.0-6.5, inclusive
5. Able to walk 25 feet in 60 seconds or less
6. Stable dose of non-excluded MS Disease Modifying Therapy for at least 6 months prior to Screening Visit (Visit 1).
7. Women of childbearing potential shall either be surgically sterile, or must agree not to become pregnant for the duration of the study. Women must be willing to undergo a serum pregnancy test at screening, and at the conclusion of the study. Participants of childbearing potential must agree to use a medically approved form of birth control (abstinence, intrauterine device (IUD), oral contraception, barrier and spermicide or hormonal implant) throughout the duration of the study and for at least 3 months following the last transplantation. For those women who are sexually active and using oral contraceptives, a second form of barrier contraception is required. Men must be willing to consistently use two forms of contraceptive if their partners are of childbearing age.
8. Capable of providing informed consent and willing and able to follow study procedures, including willingness to undergo multiple/repeated lumbar puncture.

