6. PRIOR AND CONCOMITANT THERAPY

6.1. PRIOR THERAPY

Participants who received prior cell therapy of any kind will be excluded from the study (see Section 3.2).

Study participants who begin an excluded medication during the study period will be discontinued from treatment. In order to minimize the amount and impact of missing data, study investigators will make all reasonable efforts to collect key efficacy and safety data on participants who discontinue treatment or discontinue from the study.

All medications taken prior to the first transplantation will be recorded as Prior medications.

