6.2. CONCOMITANT AND EXCLUDED THERAPY

Concomitant medications are those given to the subject during or after the first transplantation. All concomitant medications will be recorded.

Brainstorm Cell Therapeutics Ltd.	IND#018615	
Phase 2 Clinical Protocol BCT-101-US Amendment 1.1, June 2019	MSC-NTF cells (NurOwn®)	Page 36 of 59

Current use of immunosuppressive medication or use of such medication within 6 months of study enrollment (aside from approved B-cell immunotherapy) and anticoagulation therapy are exclusionary.

Alemtuzumab (Lemtrada), Cladribine (NDA submitted), Natalizumab (Tysabri), S1P modulators (such as Gilenya) high dose pulse intravenous methylprednisolone (IVMP, 1 gram) to treat a relapse within the 6 months prior to study entry or other investigative MS therapies are exclusionary due to safety considerations. However, a single dose of IVMP 100 mg as part of the Ocrevus (or Rituxan) infusion protocol q6M is not exclusionary and would be allowed in the study.

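### SAP 9.2 scores response on the observed Week 28 value, so a 25% gain after on-study pulse corticosteroid for MS, or after an excluded MS therapy begun after dose 3, counts as NurOwn response

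*SAP*

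**What the plan says.** The primary efficacy endpoint, which ranks first among the secondary endpoints, is a responder rate. SAP 9.2: "A subject will be defined as a responder to study drug if their T25FW walking speed or 9-HPT improves by 25% or more" from baseline to Week 28. One event overrides the observed value: "All deaths related to disease progression or treatment will be defined as non-responders". Missing values other than dates are not imputed (SAP 6.8). The mITT population (SAP 6.5.2) requires one transplantation and one post-baseline T25FW or 9-HPT, with no condition on medication.

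On other therapy, Protocol 6.1 says: "Study participants who begin an excluded medication during the study period will be discontinued from treatment". It adds that "study investigators will make all reasonable efforts to collect key efficacy and safety data on participants who discontinue treatment or discontinue from the study". Protocol 6.2 lists excluded therapies, but it words the steroid item as "high dose pulse intravenous methylprednisolone (IVMP, 1 gram) to treat a relapse within the 6 months prior to study entry", which concerns the period before entry. The 100 mg methylprednisolone given with a B-cell infusion is treated differently: as part of the "infusion protocol q6M is not exclusionary and would be allowed in the study". Protocol 6.2 also says: "All concomitant medications will be recorded".

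SAP 6.5.3 defines an Efficacy Evaluable (EE) population that needs all three treatments and no important deviation affecting efficacy. Appendix I, section 2, drops the key EE analyses because EE and mITT hardly differ. SAP 9.5.1 permits, but does not require, sensitivity analyses for deviations.

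**The concern.** Scoring the observed value whatever other therapy was given is a treatment-policy rule. The SAP applies it by default, without stating it, and then names the result as response to the study drug. Pulse corticosteroid and a newly started MS therapy are both given to change MS outcomes, and the rule credits any resulting gain to NurOwn.

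In a randomized trial, a control arm would carry similar exposure. Here there is none, so the contribution of another therapy cannot be separated within this rate. SAP 6.4 allows the responder percentage to be compared with matched historical controls, and Appendix I, section 5, plans a comparison with the CLIMB registry. The stated purpose of the data is to inform a later randomized study (SAP 4.3), so readers will want to know what the rate counts.

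**Working it through.** The plan gives no power, effect size or expected response rate, so there is no figure to reproduce. The check has two parts: which participants the rule can reach, and how far one of them moves the rate.

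**1. Is there a therapy rule anywhere?** SAP 9.2 has the death override only. SAP 6.5.2 has no medication condition. SAP 9.5.1 is optional and unspecified. The key EE analyses are dropped. Nothing in the SAP or Appendix I censors, excludes or reclassifies a value obtained after other MS therapy.

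**2. Who can have a Week 28 value after such therapy?** Protocol 4.9 follows treated or partly treated participants for about 12 weeks from the last transplantation. Doses fall at Weeks 0, 8 and 16.

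- Stopped after dose 1: 0 + 12 = Week 12.
- Stopped after dose 2: 8 + 12 = Week 20.
- All three doses: 16 + 12 = Week 28.

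Appendix I, section 3.1, moves early-termination data to the nearest scheduled visit. Week 20 is 2 weeks from Week 22 and 4 from Week 16, so it maps to Week 22. Week 12 is 4 weeks from both Week 8 and Week 16. Neither normally becomes Week 28. Two routes to the Week 28 endpoint remain:

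- an excluded therapy begun after dose 3 (Weeks 16 to 28), when there is no dosing left for Protocol 6.1 to stop;
- pulse corticosteroid at any time on study, because Protocol 6.2 names it only as a pre-entry exclusion and its use does not clearly stop dosing.

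**3. Shift per affected responder.** Shift = 1/n.

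- n = 20: 1/20 = 5.0 points.
- n = 18 (assumed): 1/18 = 5.6 points.
- An assumed 0, 1 or 2 affected responders of 20: 0, 5 or 10 points.

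**4. Against sampling error.** Exact (Clopper-Pearson) 95% intervals, with assumed counts:

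| Responders | Rate | 95% CI | Width |
|---|---|---|---|
| 3/20 | 15.0% | 3.2 to 37.9 | 34.7 |
| 2/20 | 10.0% | 1.2 to 31.7 | 30.5 |

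**5. Chance of at least one.** Let q be the assumed probability that a participant both receives such therapy and then shows a 25% gain at Week 28. P(at least one of 20) = 1 − (1 − q)^20. For q = 1%, 2%, 5% and 10% this is 18%, 33%, 64% and 88%. The documents give no value for q.

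**6. Registry comparison.** A rule applied to the trial side alone lowers the trial-minus-CLIMB difference by 1/20 = 5.0 points per affected responder, with the registry side unchanged.

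**The case against.** The strongest reply is that treatment policy is a legitimate choice and that very few participants are likely to be affected. Appendix I calls the difference between EE and mITT minimal. EE requires all three treatments, so few can have been stopped before dose 3. Appendix I, section 4.1, drops the separate MS relapse summary for lack of data, and the protocol ties pulse methylprednisolone to relapse. Important deviations are tabulated and listed (SAP 7.3), and medications are tabulated (SAP 7.7). Nor does any responder rate from one open-label arm isolate the drug from practice, placebo response or permitted therapy.

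Most of that stands as a limit on size. It does not remove the gap. The EE evidence is weaker for Weeks 16 to 28, where exclusion depends on a deviation being judged important. The relapse remark is ambiguous. The medication tables ignore indication, and no planned output links new MS therapy to responder status. If treatment policy is intended, the SAP should say so.

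From Protocol 6.1 a reader might infer that anyone who starts an excluded drug at any time is carried to Week 28 and scored there. The documents do not support this, because follow-up ends about 12 weeks after the last dose and early-termination data go to the nearest visit.

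Two objections to a remedy also have force. One early pulse would make a participant a non-responder months later, and deciding whether a steroid was given for MS adds judgement in an open-label study. The remedy has to answer both.

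**Conclusion.** The point holds in limited form. At Week 28 the exposure is on-study pulse corticosteroid for MS and excluded MS therapy begun after dose 3. Participants stopped earlier mainly affect the by-visit rates in SAP 9.6. The size is 5.0 points per affected responder of 20, small beside an interval about 35 points wide. The number affected is unknown and may be zero. The counts of 3 and 2 responders, the denominator of 18 and the values of q are all assumptions.

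A reader might go further and conclude that the responder rate is inflated, or that the trial's main conclusion is at risk. Neither follows. The documents report no affected participant, and the primary objective is safety. What they do show is an unstated rule whose label claims more than is counted. Correcting it is a worthwhile, low-cost improvement.

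**What to change.** In SAP 9.2, after the sentence on deaths, add:

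> A participant with an observed Week 28 value who, between V3 and that assessment, received pulse corticosteroid for MS (for example 1 g IV methylprednisolone or equivalent), or began an MS therapy excluded in Protocol 6.2, is a non-responder. The 100 mg methylprednisolone given with a B-cell infusion, and corticosteroid for non-MS reasons, do not count.

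Then specify the following:

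- **By visit.** Apply the same rule in SAP 9.6, counting therapy from V3 to the visit concerned.
- **Denominator.** Keep it the same as for the as-observed rate, so the rule does not alter how participants without a value are handled.
- **Classification.** Decide from the medication record whether a steroid was for MS, without reference to the participant's T25FW and 9-HPT results.
- **Reporting.** Always show the as-observed rate alongside, with the number affected and a listing of therapy dates. Include in the listing anyone who newly starts a permitted MS therapy. The rule does not reclassify these participants, and the entry criterion covers only the period before screening: "Stable dose of non-excluded MS Disease Modifying Therapy for at least 6 months prior to Screening Visit (Visit 1".
- **CLIMB.** Use the as-observed rate for the registry comparison unless the rule can also be applied to registry patients. Show the rule-based rate as a sensitivity analysis.

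The cost is a few SAP sentences and a review of medication records that the protocol already requires. SAP 7.7 displays medications without regard to indication, and the documents do not say whether indication is captured. Pulse is therefore defined by dose, and the MS condition needs a record check.

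The downside is that the trial rate can only stay the same or fall. A single early pulse also makes a participant a non-responder at Week 28. The as-observed rate and the dated listing keep that visible.

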9.3. Testing Statistical Assumptions Including Comparability at Baseline

Not applicable since BCT-101-US is an open label single arm study with 20 participants.

9.4. Subgroup Analyses

No subgroup analysis is planned because of the small sample size (20 subjects).

9.5. Multiple Comparisons and Multiplicity

Not applicable since BCT-101-US is an open label single arm study with 20 participants.

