3. STUDY OBJECTIVES AND ENDPOINTS

3.1. Study Objectives

3.1.1. Primary Objective

The primary objective of the study is to evaluate safety and tolerability of 3 intrathecal doses of NurOwn® (MSC-NTF cells).

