6.4. Data Presentation Conventions

Continuous variables (e.g. age) are summarized using descriptive statistics (the number of subjects with available data, the mean, standard deviation (SD), first quartile (Q1), median, third quartile (Q3), minimum and maximum).

Categorical variables (e.g. race) are summarized using counts and percentages. Percentages are calculated using the total subjects within the dose group (or dose group and relevant subgroup when appropriate) being presented.

The following conventions are applied to all data presentations and summaries.

- For continuous variables, all mean, first quartile (Q1), median and third quartile (Q3) values are formatted to one more decimal place than the measured value. Minimum and maximum values are presented with the same number of decimal places as the measured value. For measure of variation, e.g. SD, use two more decimal places than the measured value, unless numbers are in at least 100s and there are space constraints in which case 1 decimal place is fine.
- For categorical variables, the number and percentage of responses are presented in the form XX (XX.X%) where the percentage is in the parentheses.
- Date variables are formatted as DDMMYY for presentation. Time is formatted in military time as HH:MM for presentation.
- Wherever possible, data will be decimal aligned or left aligned or as appropriate to best display the data and column headers. Parenthesis will also be aligned appropriately for best display.
- Hypothesis testing to determine if changes from baseline were statistically significant and comparing these against matched historical controls will be performed and presented in select Tables either as post-text Tables or in the CSR depending upon availability of historical data. Similar additional analyses on the percentage of responders from the current study against matched historical controls may be included in the CSR. Subjects from a historical database will be selected by matching key screening or baseline characteristics.
- P-values, if applicable, will be presented to 3 decimal places. If the p-value is less than 0.001 then it will be presented as <0.001. If the rounded result is a value of 1.000, it will be displayed as >0.999.

The table and listing shells and table of contents provide the expected layout and titles of the tables, listings and figures.

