9.6. Analysis of the Secondary Efficacy Endpoints

T25FW and 9-HPT

Secondary efficacy endpoints are listed in [Section 3.2.2](#). This section provides additional details.

In addition to the primary efficacy endpoint evaluated at Week 28, the percentage of subjects with improvements from baseline to each post baseline timepoint in either T25FW or 9-HPT of $\geq 15\%$, $\geq 20\%$ and $\geq 30\%$ will also be evaluated.

Other thresholds may be considered to define responder analyses for the efficacy endpoints if the above are deemed to be too low or too high.

As indicated in [Section 3.2.2](#), in addition to determining if a subject was a responder on either T25W or 9-HPT at each timepoint, these two efficacy assessments will be separately evaluated at each timepoint to see improvements in each of them.

- Percentage of subjects who improve on T25FW by $\geq 25\%$ (Other thresholds such as $\geq 15\%$, $\geq 20\%$ and $\geq 30\%$ will also be evaluated)
- Percentage of subjects who improve on 9-HPT by $\geq 25\%$ (Other thresholds such as $\geq 15\%$, $\geq 20\%$ and $\geq 30\%$ will also be evaluated)

In order to determine the amount of change or % change from baseline to each post baseline timepoint, mean changes in T25FW from baseline to each post baseline timepoint will be summarized in addition to other descriptive statistics for continuous variables. This will be repeated for the 9-HPT. In addition, mean changes in feet per second will be summarized as noted above for the timed walk.

Biomarkers

CSF and/or serum samples will be collected for determining the concentration of neurotropic factors, inflammatory markers, miRNA, etc. collectively referred to as biomarkers.

Details of biomarker analyses will be specified subsequently.

Biomarkers to be assessed include the following:

Biomarker Type	CSF	Serum
MSC-NTF derived Neurotropic Factors	BDNF, GDNF, HGF, LIF, VEGF, TSG-6, G-CSF	BDNF, GDNF, HGF, LIF, VEGF, TSG-6, G-CSF
Inflammatory Biomarkers	MCP-1, SDF-1, CHIT-1, TNF- α , sCD27 and a full panel of cytokines, chemokines and regulatory proteins	Full panel of cytokines, chemokines and regulatory proteins
miRNA	miRNA panel	miRNA panel
Neurodegeneration	NfL, NfH, GFAP	NfL, NfH, GFAP

Expanded Disability Status Scale (EDSS)

Mean Changes and % Changes from baseline to each post baseline time point in EDSS Scores will be summarized along with other descriptive statistics for continuous variables.

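### SAP 9.5 sets multiplicity aside because the study has one arm, while SAP 9.1 and 6.4 plan several unadjusted tests at 0.05 with no order and no nominal label

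*SAP*

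**What the plan says.** SAP 9.5 disposes of multiple comparisons in one sentence: "Not applicable since BCT-101-US is an open label single arm study with 20 participants".

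Other sections plan inference:

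- SAP 9.1: "Inferential statistical tests will be performed at Type I error" 0.05, two-sided. It adds that "hypothesis testing will be performed against a historical database by selection of subjects matched on key screening or baseline characteristics".
- SAP 6.4 covers two families of tests: whether changes from baseline are significant, and comparisons with matched historical controls. These "will be performed and presented in select Tables either as post-text Tables or in the CSR depending upon availability of historical data". For responder rates the commitment is weaker: "Similar additional analyses on the percentage of responders from the current study against matched historical controls may be included in the CSR".
- SAP 3.2.2 and 9.6 list responder thresholds of 15, 20, 25 and 30% for T25FW, for 9-HPT and for improvement on either. They also list changes in many other outcomes at each post-baseline visit. Of T25FW and 9-HPT, SAP 9.6 says "these two efficacy assessments will be separately evaluated at each timepoint to see improvements in each of them". It leaves room for further thresholds.
- SAP Appendix I, section 5, says study results will be compared with a registry that holds T25FW, 9-HPT and MRI data on matched patients. Registry values are interpolated to Week 28. Section 5.1 adds separate analyses of each hand.

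SAP 9.2 designates one primary efficacy endpoint: at least 25% improvement in T25FW or 9-HPT at Week 28. Efficacy as a whole is secondary: "The primary objective of the study is to evaluate safety and tolerability of 3 intrathecal doses". No section gives a hierarchy, an adjustment, an exploratory label or a list of the tables that will carry p-values.

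**The concern.** The reason given in 9.5 does not support its conclusion. A single-arm study that tests one outcome once has no multiplicity problem. A single-arm study that tests several outcomes, thresholds and visits at 0.05 has the same problem as a randomized one. A sample of 20 does not remove it either.

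SAP 9.2 names a lead efficacy endpoint but does not say that its p-value will be read differently from any other. As written, any efficacy p-value below 0.05 could be reported as significant. Protocol 9.3.1 and SAP 4.3 say the data are to inform the design of a later randomized study. An endpoint, threshold or visit could therefore be carried into that study because it crossed 0.05 by chance among several that were tried.

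**Working it through.** **The plan's own figure.** The only stated figure is the two-sided 0.05 in SAP 9.1. It is a per-test level, so for one test 1 − 0.95¹ = 0.05 by definition. The plan gives no family-wise level, power or sample size calculation to reproduce.

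**Counting what the plan permits against historical controls.** The registry comparison exists only at Week 28 (Appendix I, section 5).

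- Responder comparisons: 3 definitions (T25FW, 9-HPT, either) × 4 thresholds = 12.
- Change and % change in T25FW (seconds), T25FW (ft/sec) and 9-HPT: 3 × 2 = 6, total 18.
- Each hand separately: 2 × 4 thresholds + 2 × 2 changes = 12, total 30.
- The MRI measures in SAP 8.7: 10, total 40.

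These are tests that could be run, not tests the plan commits to.

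**Reference value.** If the 12 responder tests were independent, the chance of at least one p < 0.05 would be 1 − 0.95¹² = 46.0%. That is too high here: the thresholds are nested and the either-measure definition is built from the other two. Simulation is needed.

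**Simulation 1: Week 28 responder tests with no true difference.** There were 20 treated patients. The documents give no control number, SD or correlation, so these are assumptions: 20, 50 or 100 exchangeable controls; normally distributed % change with mean 0 and SD 15 or 25; T25FW/9-HPT correlation 0, 0.3 or 0.6. The test was Fisher's exact, with 5,000 runs per scenario. Ranges are over the three correlations.

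| Controls | SD | Primary efficacy test alone | Any of 12 |
|---|---|---|---|
| 20 | 15 | 0.7–1.0% | 7.3–8.4% |
| 20 | 25 | 2.0–2.4% | 11.7–13.1% |
| 50 | 15 | 1.5–2.0% | 11.1–11.7% |
| 50 | 25 | 3.5–3.6% | 16.0–17.3% |
| 100 | 15 | 2.1–2.3% | 14.2–15.8% |
| 100 | 25 | 3.3–3.9% | 18.4–19.6% |

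Adding a t-test of change for each of the two measures gives about 14 to 24%.

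**Simulation 2: within-group change with no true change.** The 20 patients were analysed with one-sample t-tests on eight endpoints at four visits (Weeks 8, 16, 22 and 28), so 8 × 4 = 32 tests, with 6,000 runs per scenario. SAP 3.2.2 offers eight such endpoints: T25FW, 9-HPT, EDSS, MSWS-12, LCLA, SDMT and the two MSFC composites. Correlations are again assumed.

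| Between endpoints | Between visits | Week 28 only (8 tests) | Four visits (32 tests) |
|---|---|---|---|
| 0 | 0.5 / 0.8 | 33.1 / 33.6% | 74.8 / 63.0% |
| 0.3 | 0.5 / 0.8 | 31.1 / 30.8% | 70.1 / 57.7% |
| 0.6 | 0.5 / 0.8 | 23.4 / 23.2% | 58.2 / 45.5% |

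With zero correlation the Week 28 figure should match 1 − 0.95⁸ = 33.7%, and it does within simulation error. All rates count false positives in either direction.

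**The case against.** The strongest reply is that the plan promises less testing than its list of outcomes suggests, and much of this stands. SAP 6.4 restricts tests to selected tables and makes them depend on historical data. Responder comparisons are optional. Most of SAP 9.6 describes summaries, and a tabulated percentage is not a test. The study is a 20-patient proof of concept with safety as its primary objective. Its lead efficacy endpoint, visit and threshold are fixed in advance.

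Two stronger readings are tempting, and the documents support neither.

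- A reader might multiply measures by thresholds by visits and conclude that dozens of tests against historical controls are planned. The number of tests is never stated. Appendix I interpolates registry values to Week 28 only and describes no control values for the earlier visits.
- A reader might conclude that the stated Type I error is wrong. It is a per-test level, and no family-wise level is claimed. Testing other outcomes does not change the error rate of the designated primary efficacy test. Whether 0.05 holds for that test depends on the test chosen, the matching and the linear interpolation, which are separate questions.

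The reply does not rescue 9.5. SAP 9.1 and 6.4 still say that tests will be performed, and SAP 6.4 includes within-group tests of change. Nothing says which p-values are formal. A small study with safety as its primary objective justifies a light remedy, but not declaring the issue inapplicable.

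**Conclusion.** The point holds in limited form. The rationale in SAP 9.5 is mistaken and conflicts with the testing planned in 9.1 and 6.4. The designated Week 28 test is not inflated: it stays at 0.7 to 3.9% in the simulations. Across the efficacy tests the plan permits, 0.05 does not hold. The chance of at least one false positive is about 7 to 20% for the 12 Week 28 responder comparisons. For within-group change in eight endpoints it is about 23 to 34% at Week 28 and 45 to 75% over four visits.

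These sizes rest on assumed control numbers, SDs and correlations and on controls exchangeable with the treated patients. They apply only if the tests are actually run. The two MSFC composites share components with other endpoints, so true correlations may be higher than assumed and the within-group rates somewhat lower. The direction does not depend on these choices: every scenario with several tests exceeded 5%. This is a cheap improvement to the plan, not a flaw in its lead analysis.

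**What to change.** Replace the text of SAP 9.5 with a statement such as:

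*The only formal hypothesis test, at two-sided 0.05, compares the Week 28 responder rate (at least 25% improvement in T25FW or 9-HPT, mITT population) with the matched registry controls. All other endpoints, thresholds, visits, separate-hand results, MRI measures and within-group changes are reported as estimates with 95% confidence intervals. Any p-values for them are nominal and will not be used to claim statistical significance. The tables that carry p-values are listed here.*

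No alpha adjustment, new data or design change is needed. The cost is one paragraph, a short list of tables, and the sponsor's freedom to call secondary results statistically significant. SAP section 2 allows further changes to be finalized before database lock.
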